6.1. Overall Design

Study I8Q-MC-GSEA (GSEA) is a first-in-man, Phase 1, randomized, double-blind, placebo-controlled, 2-part, ascending single- and multiple-oral dose study of LY3202328 in statin-free, overweight, healthy subjects (Part A) and in statin-free, overweight, dyslipidemic subjects with a statin DDI assessments (Part B).

This study will be conducted in 2 parts: Part A, a SAD study design at a single site and Part B, a MAD study design conducted in multiple sites.

Figure GSEA.1 illustrates the study design.

Part A: Single Ascending Dose

Cohort	N	Week								
		1	2	3	4	5	6	7	8	9
		Period 1		Period 2		Period 3			Period 4 (Food Effect)	
1	3	1 mg LY		10 mg LY		Placebo	D/C ^a			
	3	1 mg LY		Placebo		100 mg LY	D/C ^a			
	3	Placebo		10 mg LY		100 mg LY	D/C ^a			
2	3		3 mg LY		30 mg LY		Placebo		30 mg LY ^b	D/C ^a
	3		3 mg LY		Placebo		300 mg LY		Placebo ^b	D/C ^a
	3		Placebo		30 mg LY		300 mg LY		30 mg LY ^b	D/C ^a

Part B: Multiple Ascending Dose

Cohort	N	Week													
		3	4	5	6	7	8	9	10	11	12	13	14		
3	10	Period 5													
		SS/AS ^c	5 mg LY or placebo ^d	SS/AS + 5 mg LY or placebo ^e	D/C ^f										
4	10										Period 6				
		SS/AS ^c	20 mg LY or placebo ^d	SS/AS + 20 mg LY or placebo ^e	D/C ^f										
5	10										Period 7				
		SS/AS ^c	100 mg LY or placebo ^d	SS/AS + 100 mg LY or placebo ^e	D/C ^f										
6	10										Period 8				
		SS/AS ^c	300 mg LY or placebo ^d	SS/AS + 300 mg LY or placebo ^e	D/C ^f										

Abbreviations: AS = atorvastatin; CRU = clinical research unit; D/C = discharge (from the CRU); LY = LY3202328; N = number of subjects; SS = simvastatin.

- a Discharge from the CRU will occur on Day 2 with Follow-up visits to occur on Days 3 and 5.
- b LY3202328 or placebo will be administered with food.
- c A single dose of simvastatin or atorvastatin will be administered on Day -7.
- d Multiple doses of LY3202328 or placebo will be administered daily on Days 1 through 28.
- e LY3202328 or placebo will be coadministered with simvastatin or atorvastatin on Day 29.
- f Discharge from the CRU will occur on Day 30 with Follow-up visits to occur on Days 35 and 56.

Note: The doses for Part B are subject to change and will not exceed the maximum tolerated dose from Part A (starting as low as 5 mg and not to exceed 300 mg).

Figure GSEA.1. Study design for Protocol I8Q-MC-GSEA.

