6.1.1. Part A: Single Ascending Dose with Food Effect Design

Part A will comprise a double-blinded, 2-staggered, alternating, 3- or 4-period sequence design of single ascending doses in statin-free, overweight (body mass index [BMI] 25.0 to 35.0 kg/m²),

healthy male and female subjects, investigating the safety, tolerability, and PK of single doses of LY3202328 administered in the fasted state. One dose level will be repeated in the fed state using the same randomization as conducted in the fasted state to assess the effect of food on LY3202328 exposure.

A total of 18 subjects will be enrolled in 2 cohorts. Cohort 1 will consist of 3 periods at dose levels 1, 10, and 100 mg, and Cohort 2 will consist of 3 periods at dose levels 3, 30, and 300 mg. A fourth dosing period will be added to either Cohort 1 or Cohort 2 to assess exposure differences when LY3202328 is administered in a fed state. Each cohort will consist of 9 subjects where subjects will receive either a single LY3202328 dose or a corresponding placebo in alternating ascending order.

In each cohort, 6 subjects will receive LY3202328 and 3 subjects will receive placebo. Subjects will be dosed in the fasted state in all periods except for subjects in the cohort that will return for the fourth dosing period to repeat 1 dose level (planned 30 mg dose level) in the fed state to evaluate food effects on LY3202328 exposure. An additional potential cohort (not evaluated for food effect) will be reserved for the fourth dosing period at a higher dose level (600 mg). Escalation to this higher dose will only be made if exposure continues to increase between 100 and 300 mg dose levels and the safety profile supports dosing to a higher level.

Potential subjects will be screened to assess their eligibility to enter the study within 42 days prior to study entry (i.e., prior to Check in for Part A). Subjects will be confined at the clinical research unit (CRU) from Day –1 (the day before dosing) to Day 2 (24 hours postdose), and return on Days 3 and 5 (48 and 96 hours postdose, respectively) for follow-up assessments. Dosing in subsequent periods will be approximately 2 weeks after dosing in the prior period, with subjects dosed on Day 1 of Week 1, 3, or 5 (Cohort 1); Week 2, 4, or 6 (Cohort 2); and Week 8 (food effect period, Cohort 2).

Treatment of the cohorts in Part A will be staggered so that the appropriateness of escalation to the next dose level can be determined from the current dose level.

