10.2.1. Serious Adverse Events

An SAE is any AE from this study that results in one of the following:

- death
- initial or prolonged inpatient hospitalization
- a life-threatening experience (that is, immediate risk of dying)
- persistent or significant disability/incapacity
- congenital anomaly/birth defect
- events considered significant by the investigator based upon appropriate medical judgment

Study site personnel must alert Chorus, or its designee, of any SAE within 24 hours of investigator awareness of the event via a sponsor-approved method. If alerts are issued via telephone, they are to be immediately followed with official notification on study-specific SAE forms. This 24-hour notification requirement refers to the initial SAE information and all follow-up SAE information.

Although all AEs are recorded in the CRF after signing informed consent, SAE reporting begins after the subject has signed informed consent and has received investigational product.

However, if an SAE occurs after signing informed consent, but prior to receiving investigational product, AND is considered "reasonably possibly related" to a study procedure then it MUST be reported.

Investigators are not obligated to actively seek AEs or SAEs in subjects once they have discontinued from and/or completed the study (the subject summary CRF has been completed). However, if the investigator learns of any SAE, including a death, at any time after a subject has been discharged from the study, and he/she considers the event reasonably possibly related to the study treatment or study participation, the investigator must promptly notify Chorus.

Pregnancy (maternal or paternal exposure to investigational product) does not meet the definition of an AE. However, to fulfill regulatory requirements any pregnancy should be reported following the SAE process to collect data on the outcome for both mother and fetus.

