6.1.2 Fasting Lipid Profile Analyses in Part B

Fasting lipid profiles will be collected from all subjects in Part B just prior to dosing on the day of dosing, Day 7, Day 14, Day 21, and Day 28, and 7 (Day 35) days after stopping dosing of the randomized treatment. An additional follow-up assessment will be collected 14 (Day42) or 28 (Day 56) days after stopping dosing of the randomized treatment for Cohort 3 (5mg QD) and Cohorts 4 through 6, respectively.

A last on-treatment observation measurement will be derived for each subject using the last post-dose measurement for a lipid parameter taken while the subject is taking study medication during the 28-day treatment period. Change from baseline for each of the lipid parameters will be derived for each of the post-dosing time points (Days 7, 14, 21, 28, 35, and 42 or 56) and the last on-treatment observation using the pre-dose measurement from the first day of dosing as the baseline.

Descriptive statistics for the measurement at baseline and the measurement and change from baseline at each post-baseline time point plus the last observation will be tabulated.

An MMRM analysis will be conducted for each lipid parameter using the change from baseline values from Days 7, 14, 21, 28, 35, and 42. The MMRM model for change from baseline will contain fixed effects for treatment, time, and their interaction, a random effect for subject, and the baseline measurement as a covariate. Since the time points are evenly spaced the covariance structure among the repeated measurements for a subject will be assumed to be common across subjects and modeled using a autoregressive(1) 7x7 matrix. Satterthwaite's approximation will be used to estimate denominator degrees of freedom. Any missing assessments will be assumed to be missing at random, so estimates of treatment effects from the model will be unbiased.

These analyses will be performed using the SAS procedure PROC MIXED. The tabular output for these MMRM analyses will present the least squares means, standard errors and 95% confidence intervals and Type 3 p-values for each main effect marginal. Pairwise contrasts of the least squares means between the LY dose levels and placebo along with the associated 95% confidence interval and Type 3 p-values will also be provided at each time point using LSMESTIMATE statements.

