7.2 Adverse Events

Investigators will monitor the safety of subjects and will be responsible for their medical care during the study. The investigator will interpret and document adverse events and will indicate whether each event is serious and the strength of causality to the study medication. The subject will be followed until adverse events are resolved.

Only those adverse events (AE) that emerge or worsen after the date of first dose of study medication, i.e. treatment emergent adverse events (TEAE), will be summarized. Adverse events with a missing start date will also be classified as TEAE.

Summaries of TEAE will include the number of subjects with at least one TEAE for each treatment group. When reporting by system organ class (SOC) and preferred term (PT), the reports will present the SOC in alphabetical order; while PTs within the SOC will be presented in order of overall decreasing frequency of occurrence in the combined LY treatment groups. A subject with multiple TEAEs (different PTs) coded to the same SOC will be counted only once for that SOC, but will be counted each time for different PTs within that SOC. A subject with separate events of the same PT (different start/stop dates) will be counted only once in the frequency tables for that PT.

In Part A, TEAEs will be reported using the treatment that the subject most recently received. Adverse events that occur on the first day of a dosing period will be assigned to the treatment received on that day.

No statistical testing will be performed for comparisons of TEAEs.

An overview of all TEAEs for both Parts A and B will also be provided by treatment group using the types of TEAEs defined in the following subsections.

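### Part A TEAEs are credited to the most recent treatment with no end of window, so each cohort's final period has about 4 days of AE observation against about 14 in earlier periods

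*SAP*

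**What the plan says.** **Which events count.** SAP 7.2 opens the TEAE window with "Only those adverse events (AE) that emerge or worsen after the date of first dose of study medication" and gives no closing date. For Part A it adds: "In Part A, TEAEs will be reported using the treatment that the subject most recently received". The definition in Protocol Appendix 1 refers to a treatment period, but neither document fixes the length of that period for the AE tables. No exposure-adjusted rate is planned.

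**Part A calendar.** Protocol 6.1.1: "Dosing in subsequent periods will be approximately 2 weeks after dosing in the prior period". Cohort 1 is dosed in Weeks 1, 3 and 5, and Cohort 2 in "Week 2, 4, or 6 (Cohort 2); and Week 8 (food effect period, Cohort 2". After each dose subjects "return on Days 3 and 5 (48 and 96 hours postdose, respectively) for follow-up assessments". Footnote a of Figure GSEA.1 (Protocol 6.1) says the same for discharge: "Discharge from the CRU will occur on Day 2 with Follow-up visits to occur on Days 3 and 5". Protocol 9.2 places the Part A end-of-study procedures at Day 5. After that, Protocol 10.2.1 applies: "Investigators are not obligated to actively seek AEs or SAEs in subjects once they have discontinued from and/or completed the study".

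**Optional 600 mg.** SAP 2.1 places it in Cohort 1 Period 4; Protocol 6.1.1 makes it conditional on exposure and safety. SAP 7 counts a second placebo administration in the fourth period as a separate subject.

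**Part B calendar.** SAP 6.1.2 schedules the last follow-up "14 (Day42) or 28 (Day 56) days after stopping dosing of the randomized treatment for Cohort 3 (5mg QD") and for Cohorts 4 to 6, respectively. SAP 7.3.2, 7.4.3 and 7.5.2 also list Day 42 or 56. SAP 7.4.2 lists only Days 35 and 42. Protocol 6.1.2 gives Days 35 and 56 (168 and 672 h) for all cohorts, but the Part B schedule in Protocol Appendix 2 labels Day 56 as 336 h.

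**The concern.** The number and severity of TEAEs, summarised by dose group, form part of the primary endpoint (Protocol 11.3.1.2). The SAP tabulates the number of subjects with a TEAE, total event counts and maximal severity by treatment. All of these grow with time under observation.

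An event 10 days after a mid-sequence dose is credited to that dose. The same event 10 days after a subject's last dose falls after the final visit, when nobody is required to look for it. A group whose doses all fall in a final period can therefore show fewer TEAEs than placebo or lower doses through the calendar alone. In Part A this affects the last dose level given in Cohort 1, which is where a reader looks for emerging intolerance, and the contrast of 30 mg fed with 30 mg fasted.

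**Working it through.** **Step 1. Window lengths, Part A.**
- Cohort 1: 7 × (3 − 1) = 14 and 7 × (5 − 3) = 14 days between doses.
- Cohort 2: 14, 14 and 14 days (Weeks 2, 4, 6, 8).
- After the last dose in either cohort: 96 h / 24 = 4 days.
- Ratio: 14 / 4 = 3.5. At a constant background rate, expected background event counts differ by the same factor.

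**Step 2. Who has which window.** Each active dose level has 6 administrations.

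| Group | No 600 mg period | 600 mg as Cohort 1 Period 4 |
|---|---|---|
| 1, 3, 10, 30 fasted, 300 mg | 6 × 14 = 84 subject-days each | 84 each |
| 100 mg | 6 × 4 = 24 | 6 × 14 = 84 |
| 600 mg | not given | 6 × 4 = 24 |
| 30 mg fed | 6 × 4 = 24 | 24 |
| Placebo | 15 × 14 + 6 × 4 = 234 over 21 | 18 × 14 + 6 × 4 = 276 over 24 |
| Placebo mean | 234 / 21 = 11.1 days | 276 / 24 = 11.5 days |

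Without 600 mg, placebo has 6 administrations at 14 days and 3 at 4 days in Cohort 1, and 9 at 14 days and 3 at 4 days in Cohort 2. The right-hand column assumes that 600 mg follows 100 mg by the usual two weeks; the documents give no week for it.

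**Step 3. Illustration with no drug effect.** The documents give no background AE rate, so the 14-day incidence p is assumed. With a constant hazard, the 4-day incidence is 1 − (1 − p)^(4/14).

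| Assumed p, 14 days | 4-day incidence | Difference × 6 subjects |
|---|---|---|
| 20% | 6.2% | 0.8 |
| 30% | 9.7% | 1.2 |
| 40% | 13.6% | 1.6 |

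At p = 30% and without 600 mg, pooled placebo would show (15 × 0.30 + 6 × 0.097) / 21 = 24%. That lies between the 14-day and 4-day groups.

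**Step 4. Part B.** Counting from Day 28, as both documents do:
- SAP 6.1.2: 28 + 14 = Day 42 for Cohort 3; 28 + 28 = Day 56 for Cohorts 4 to 6.
- Protocol 6.1.2: 28 + 672/24 = Day 56 for all.
- Protocol Appendix 2: 28 + 336/24 = Day 42, under a column headed Day 56.

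If the SAP schedule stands, 5 mg has 56 − 42 = 14 days less (25%), and pooled placebo averages (2 × 42 + 6 × 56) / 8 = Day 52.5. On an assumed 50% with an AE by Day 56, the Day 42 figure is 1 − 0.5^(42/56) = 40.5%, a difference of 8 × 0.095 = 0.8 subject.

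**Step 5. With common windows.** At 96 h in Part A and Day 35 in Part B, every group including placebo has the same planned window, so the ratio is 1.0 in both parts. At the projected half-life of 6 to 8 h (Protocol 4.2), 96 h spans 96/8 = 12 to 96/6 = 16 half-lives.

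**The case against.** The case for leaving the tables alone has substance.

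- **They are descriptive.** SAP 7.2 plans no testing of TEAEs, and the study is not powered. Escalation uses safety data to Day 5 in Part A and Day 14 in Part B (Protocol 8.3.1), so dose decisions already rest on common windows. This stands, and it limits the severity of the point.
- **Ascertainment is not even.** Confinement and the Day 3 and Day 5 visits are the same in every Part A period. The extra 10 days are outpatient, with no scheduled visit before the next check-in, so a constant hazard may overstate the difference. This stands as a caution on the illustration.
- **Acute drug effects should fall inside 96 h.** If the projected half-life holds, the distortion is mainly in background or late events. This stands, but a background excess in the comparators is enough to make a group with a short window look cleaner than placebo.
- **A common window pushes late events out of the main rows**, which matters in a first-in-human study. This is a fair cost, and it is why those events need their own row in the same tables.

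Two stronger readings are tempting. A reader might infer that TEAE incidence is not comparable across doses at all, or that the 300 mg dose is under-observed. The calendar does not support either. The last dose in Cohort 2 is the 30 mg fed period, so 300 mg keeps about 14 days and is comparable with 1, 3, 10 and 30 mg fasted. In Part B, 20, 100 and 300 mg share one window under either document.

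**Conclusion.** The point holds for specific groups. Following SAP 7.2 as written, 100 mg (or 600 mg in its place, if given as Cohort 1 Period 4), 30 mg fed, and the placebo given in those periods have about 4 days of AE observation against about 14 elsewhere. Pooled placebo mixes the two, averaging 11.1 days, or about 11.5 with a 600 mg period. TEAE incidence and counts for these groups cannot be read against the 14-day groups.

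The window lengths come from the documents. The size in subjects, roughly 1 in 6, rests on an assumed 14-day background incidence of 20 to 40% and a constant hazard.

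For Part B, a reader might infer that 5 mg is definitely followed for 14 days less. The documents do not settle that: the Day 42 end for Cohort 3 is in the SAP only, the protocol text gives Day 56 for everyone, and the protocol schedule and SAP 7.4.2 add further conflict. These passages must be reconciled. Planned dosing, Days 1 to 29, is equal in all cohorts either way.

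This should be fixed before unblinding. It does not threaten escalation decisions or any formal test.

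**What to change.** In SAP 7.2:

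1. **Part A:** base the by-dose TEAE tables on onset from dosing to 96 h (the Day 5 visit) in every period. Laboratory tests, vital signs and ECGs already end there (SAP 7.3.1, 7.4.1, 7.5.1).
2. **Part B:** base them on onset from first dose to Day 35 in every cohort, a visit that both documents give to all cohorts.
3. Show later-onset events in a separate row of the same tables, by most recent treatment in Part A, and keep all events in the listings.
4. State the planned observation time per group in each table.

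Separately, reconcile the Day 42 and Day 56 entries across SAP 6.1.2, SAP 7.4.2, Protocol 6.1.2 and the Part B schedule in Protocol Appendix 2.

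The cost is SAP wording and one date filter, with no new data. The downside is that late-onset events leave the main rows; the separate row and the listings keep them visible.

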7.2.1 Treatment-Emergent Adverse Events

For both Parts A and B, TEAEs will be summarized by SOC and PT for each treatment group. These reports will also present the total number of TEAE for each SOC and PT, since this information is needed for reporting on clinicaltrials.gov. In addition, a presentation of TEAE preferred terms by decreasing frequency will be provided. The sort order for the table will be based on the number of subjects in the combined LY treatment groups who had the TEAE.

7.2.2 Serious Treatment-Emergent Adverse Events

A serious TEAE (SAE) is a TEAE that met one or more of the following criteria:

- Is fatal
- Is life-threatening
- Requires or prolongs hospitalization
- Is significantly or permanently disabling or incapacitating
- Constitutes a congenital anomaly or a birth defect or
- Jeopardizes the subject and may require medical or surgical intervention to prevent one of the above outcomes

For both Parts A and B, SAEs will be summarized for each treatment arm by SOC and PT for the Safety population. These reports will also include the total number of SAE for each SOC and PT. A listing of all SAE will also be provided. The listing will include the criteria that a TEAE met to be declared an SAE.

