6.1.2. Part B: Multiple Ascending Dose – Drug-Drug Interaction Design

Part B will comprise a double-blinded, MAD, staggered parallel design in dyslipidemic (TG: 150 to 499 mg/dL; LDL-c: 100 to 200 mg/dL), statin-free, overweight (BMI 27.0 to 40.0 kg/m²), male and female subjects investigating the safety, tolerability, and PK of multiple doses of LY3202328 and the effect of LY3202328 on simvastatin and atorvastatin exposure.

A total of 40 subjects will be enrolled and divided evenly into 4 study periods (n=10 subjects per study period) to evaluate 4 dose levels of LY3202328 (Periods 5, 6, 7, and 8 at 5, 20, 100, and 300 mg, respectively, are planned).

Within each cohort, 5 subjects will be stratified to the simvastatin DDI assessment and 5 subjects will be stratified to the atorvastatin DDI assessment. Within each stratum subjects will be randomly assigned 4:1 to receive LY3202328 or placebo so that 8 subjects will receive LY3202328 and 2 subjects receive placebo in each cohort. Subjects will receive QD dose of LY3202328 or placebo in the morning in the fasted state for 29 total days. For DDI assessment, subjects will also receive a single atorvastatin or simvastatin dose a week prior to LY3202328 treatment initiation, and on Day 29 after initiation of LY3202328 daily dosing (coadministered with LY3202328).

The dose levels intended for study in Part B may change based upon data from Part A, but will range from as low as 1 mg and are not to exceed the highest dose evaluated in Part A. Any dose level used in Part B will not start until the safety data from the same or higher dose level in Part A has been reviewed by the safety committee responsible for dose escalation decisions.

Potential subjects will be screened to assess their eligibility to enter the study within 42 days prior to study entry (i.e., prior to Check in for Part B). For each cohort, subjects will be admitted to the CRU on Day –8 (the day before administration of a single dose of simvastatin or atorvastatin) and will be discharged 24 hours postdose (Day –6).

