11.3.1. Safety Analyses

11.3.1.1. Clinical Evaluation of Safety

All LY3202328 and protocol procedure AEs will be listed, and, if the frequency of events allows, safety data will be summarized using descriptive methodology.

The incidence of symptoms for each treatment will be presented by severity and by association with investigational product as perceived by the investigator. Symptoms reported to occur prior to study entry will be distinguished from those reported as new or increased in severity during the study. Each symptom will be classified by the most suitable term from the current medical regulatory dictionary. Severity of the AE will be assessed according to the "Toxicity Grading Scale for Healthy Adult and Adolescent Volunteers Enrolled in Preventive Vaccine Clinical Trials 2007".

The number of investigational product-related SAEs will be reported.

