7.2.3 TEAE Resulting in Death

If there are any TEAE that result in death for either part of the study, then a listing of all deaths will be provided for that part of the study.

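### SAP 7.2.2 counts only serious TEAEs as SAEs, so a Part B SAE starting between the Day -7 statin dose and the first LY or placebo dose enters no SAE table or listing that the SAP describes

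*SAP*

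**What the plan says.** SAP 7.2 limits the adverse event summaries to TEAEs: "Only those adverse events (AE) that emerge or worsen after the date of first dose of study medication". An event with no start date is also treated as a TEAE.

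SAP 7.2.2 then builds the SAE from the TEAE: "A serious TEAE (SAE) is a TEAE that met one or more of the following criteria". The SAE tables and the SAE listing both use this definition, and of the listing the SAP says: "The listing will include the criteria that a TEAE met to be declared an SAE".

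SAP 7.2.3 makes the death listing conditional: "If there are any TEAE that result in death for either part of the study, then a listing of all deaths will be provided".

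Protocol 6.1.2 describes the Part B sequence: "subjects will also receive a single atorvastatin or simvastatin dose a week prior to LY3202328 treatment initiation". Protocol 8.1 counts the statins among the Part B study drugs. Protocol 10.2.1 has all AEs recorded in the CRF once consent is signed, and requires an SAE before investigational product to be reported if it is reasonably possibly related to a study procedure. Protocol 11.3.1.1 adds: "All LY3202328 and protocol procedure AEs will be listed".

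The last seriousness criterion in Protocol 10.2.1 is: "events considered significant by the investigator based upon appropriate medical judgment". In its place, the SAP's sixth criterion asks for jeopardy to the subject and a possible need for intervention to avert one of the other serious outcomes.

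**The concern.** SAE and TEAE are different concepts. Seriousness concerns outcome, and treatment emergence concerns timing. Making the first a subset of the second means that a serious event before the TEAE clock starts is not an SAE for any output the SAP describes.

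In most trials that affects only screening. In Part B it also affects a week in which every subject has taken a statin because the protocol requires it, and has had serial blood sampling. A serious event in that week may well stop the subject before LY or placebo. SAP 3.2 foresees subjects who are randomized but never given LY or placebo. If study treatment in SAP 2.2.1 means LY or placebo, such a subject is also outside the Safety Population on which the SAE tables are built.

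At stake is whether the safety report shows a serious event that the site recorded and that may be attributable to a study drug or a study procedure.

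**Working it through.** **Step 1. When does study medication start?** SAP 7.2 does not define the term, so it has to be inferred.
- SAP section 5 ties the first dose of randomly assigned treatment to LY or placebo, and sets the statins apart.
- SAP 7.1.1 gives exposure = date of last dose − date of first dose + 1, with a top category of 29 days.
- LY/placebo clock, Day 1 to Day 29: 29 − 1 + 1 = **29 days**. This reproduces the SAP's category.
- Statin clock, Day -7 to Day 29, with no Day 0: 7 + 29 = **36 days**. This does not fit.

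Study medication therefore starts on Day 1 with LY or placebo.

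**Step 2. Follow one event through the SAP.** Take an SAE with recorded onset on Day -5 that does not worsen after Day 1.
- SAP 7.2: not a TEAE, so it is not summarised.
- SAP 7.2.2: not a serious TEAE, so it is in neither the SAE tables nor the SAE listing.
- SAP 7.2.3: if fatal, it is listed only if a Part B TEAE is also fatal, because a fatal TEAE is what triggers the listing.
- SAP 7.2.4: the by-subject listing covers TEAEs leading to study drug discontinuation, so the event is not there.
- SAP 3.2: if the subject never receives LY or placebo, the discontinuation reason appears in a data listing, but not as an SAE.

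**Step 3. Size of the window.** Inputs: 40 planned Part B subjects (4 cohorts × 10); statin on Day -7; first LY or placebo dose on Day 1; last follow-up on Day 56.
- Day -7 to Day -1 = 7 days per subject.
- 40 × 7 = **280 subject-days**.
- Day -7 to Day 56, with no Day 0: 7 + 56 = 63 days; 7/63 = **11%**.
- SAP 6.1.2 ends follow-up of Cohort 3 at Day 42. Then 280/(280 + 10 × 42 + 30 × 56) = 280/2380 = **12%**.

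**Step 4. Seriousness criteria side by side.** The other criteria correspond: death, threat to life, hospitalisation, disability and congenital anomaly. The sixth does not. An event that the investigator judges significant, but that neither puts the subject in jeopardy nor may need intervention, meets the protocol's list and not the SAP's.

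**The case against.** The strongest defence is that the SAP's tables do what the primary endpoint asks. Protocol 11.3.1.2 defines that endpoint after administration of LY or placebo, and a clock that starts at that dose implements it. This stands: the TEAE counts for LY versus placebo are correct. A reader might infer that the counts are wrong whichever way study medication is read, because a statin clock would charge statin-only days to LY dose groups. The SAP's own exposure category rules that clock out, so this is a reason to write the definition down, not evidence of a miscount.

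A reader might also infer that the death listing holds TEAE deaths only. It does not: a fatal TEAE is the trigger, and the content is then all deaths in that part of the study. The gap is a statin-week death with no fatal TEAE in Part B.

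Nor can it be shown that a statin-week SAE would be missing from the whole report. SAP 7.2 restricts what is summarised, and Protocol 11.3.1.1 still promises a listing. SAP 1.1 places output formats in companion documents, and SAP section 10 defers additional non-PK DDI analyses to a separate plan. Neither was available. But those formats are for outputs the SAP describes, and it describes no such listing. The deferral covers additional analyses, while the SAE and death rules are set here.

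On seriousness, SAP 7.2 does say that the investigator indicates whether each event is serious. That softens the mismatch in the sixth criterion but does not remove it.

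**Conclusion.** The point holds for what the SAP describes. A Part B SAE with a recorded onset between the Day -7 statin dose and the first LY or placebo dose enters no SAE table or listing set out there, unless it worsens after that dose. A death in that week is listed only if a Part B TEAE is also fatal. The SAP thus describes no listing that carries out the commitment in Protocol 11.3.1.1 for these events, or that shows the pre-dose procedure-related SAEs that Protocol 10.2.1 requires to be reported. The site's duty to report them is unaffected. The different sixth seriousness criterion is a secondary inconsistency.

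The window is about 280 subject-days, 11 to 12% of the time from Day -7 to the end of follow-up. Larger shares come from stopping the count at Day 29: 280/(280 + 40 × 29) = 280/1440 = 19%, or 7/29 = 24% on a statin clock. Neither is a fair measure, because SAP 7.2 sets no end to the TEAE window and follow-up continues to Day 56.

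The conclusion assumes 40 subjects as planned, the LY/placebo meaning of study medication from Step 1, and no contrary listing in the companion documents or the separate plan. It does not imply that a statin-week AE comparison was owed. The DDI objective concerns statin exposure, and no objective compares AEs after the two statin doses.

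**What to change.** 1. State in SAP 7.2 that study medication means LY or placebo, so that TEAEs start at the first such dose.
2. In SAP 7.2.2 and 7.2.3, have the listings cover all SAEs and all deaths from informed consent, without the fatal-TEAE trigger. Keep the TEAE tables as they are.
3. Take seriousness from the investigator's decision under Protocol 10.2.1, and align the sixth criterion with it.
4. Flag each listed event as pre-treatment, statin alone (Day -7 to first LY or placebo dose) or treatment-emergent, and include subjects who received only the statin.

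A table of statin-week AEs by statin is optional.

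The cost is SAP wording, one flag in the adverse event data set and wider listings. The events are already recorded from consent, so no new data are needed.
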